5. GOVERNANCE

The PHCTBN is managed by the PIs ([name] and [name]) and the PHCTBN Steering Committee ([name], [name], [name], [name], [name], [name], and [name]). In order for samples/information to be shared with researchers, an IRB-approved protocol will need to be provided and the Steering Committee in conjunction with the PIs will make determinations about allocation of samples/information to researchers.

6. DATA AND SAFETY MONITORING PLAN

A meeting of the Data and Safety Monitoring Board was held on June 1, 2015. The Data Safety Monitoring Board consisted of DSMB Chair, [name], [name], [name], and [name]. The board reviewed and discussed the protocol. It was decided that since this is a low-risk, non-interventional study, it does not require a DSMB according to the NIH guidelines. Therefore, the DSMB has been eliminated.

Data and Safety will continue to be monitored by the study Principal Investigators.

7. DATA SHARING

Indiana University School of Medicine (IUSM) as well as all the participating institutions are committed to supporting the NIH Statements on Sharing Research Data and on Availability of Research Results: Publications, Intellectual Property Rights, and Sharing Research Resources. These Universities have used a variety of means as appropriate and expeditious to share data resulting from sponsored projects with colleagues, such as depositing data on a secure web-accessible data warehouses or arranging distribution of data, reagents, targets, and protocols to other researchers using established mechanisms and repositories. IUSM, and all participating institutions are signatory to the Uniform Biological Materials Transfer Agreement and will use the simple letter agreement to distribute appropriate research materials to the research community. The availability of data sharing will be publicized by individual investigators in publications and presentations.

The Universities will assure the timely release and sharing of data no later than the acceptance for publication of the main findings from final datasets, and will protect the rights and privacy of human subjects who participate in NIH-sponsored research by redacting all identifiers, and adopting other strategies to minimize risks of unauthorized disclosure of personal identifiers in accordance with authorization and consent documents. The Universities agree that data sharing is essential for expedited translation of research results into knowledge, products, and procedures to improve human health.

In addition, for this proposal, data from future research studies that may include, but are not limited to Genomics, Proteomics, and Metabolomics will also be shared through the same mechanism. These analyses will generally be performed at one of the six participating sites in the Pediatric HCT Bio-repository Network (PHCTBN). On occasion, the analyses of research samples will involve collaborators at other institutions in order to have access to the most technologically advanced or cost effective techniques. All samples analyzed at another institution as part of this project will be maintain the bar code assigned to the subject on enrollment in this study. This process allows for use of a unique identifier that the principal investigators of this study may use to link the data to other subject information but eliminates the possibility of transmission of privileged health information. Samples analyzed at another center will generally be entirely consumed by the research procedures. Any residual will be destroyed at the end of this project or returned to the Indiana University storage facility.

With respect to licensing patented inventions developed through this project, the Universities expect to elect title to inventions made with federal funds by their investigators, as appropriate under the Bayh-Dole Act, and in accordance with the NIH policy. The Universities understand that the NIH encourages the filing of patent applications on unique research resources if doing so will aid in the prompt commercialization of diagnostic, prognostic or therapeutic products. Since institutional ownership of such inventions may be of concern to collaborators, especially those who are the source of proprietary biomarkers, reagents, and/or technologies, the Universities will develop agreements with third party collaborators that assure them both adequate patent coverage and opportunities to license such patent rights, as appropriate. This agreement will be implemented in a manner that does not restrict research use by the scientific community, both nonprofit and for profit, but promotes and facilitates their active involvement in this project.

Genomic Studies

DNA from patients might be used in high-throughput genomic studies (including potentially genome-wide association studies or sequencing) for a future project.

We plan to deposit both the phenotype and genotype data obtained from the work proposed in this project into the NIH genotype and Phenotype Database that is managed by the National Center for Biotechnology Information (NCBI). The NIH genotype and

Phenotype Database collects well curate data (clinical and genetics). All the data planned for submission will be deidentified/HIPAA compliant and has been properly consented with IRB approvals.

We also plan to release the data to qualified researchers who wish to collaborate with the investigators involved in this proposal. The data will be available through a secure FTP site maintained by the University's IT department, or sent by encrypted physical media via trackable mail.

Sharing Model Organisms N/A

8. STATISTICAL CONSIDERATION

7.1. Accrual

Accrual will be monitored within each center with the expectation that the enrolled patient population is representative of the transplanted patient population at each center. Representation will be examined by comparing gender, race, ethnicity and age distributions. Accrual of minority patients will be expected to be in proportion to the number of minorities patients transplanted at each center.

7.2. Primary and Secondary Endpoints

Appendix C will detail sample size and statistical analysis to be performed

9. APPENDIX A: HUMAN SUBJECTS

Subject consent: Candidates for the study will be defined as patients receiving an allogeneic hematopoietic stem cell, cord blood, or bone marrow transplant, or T cell depleted marrow can be included. The principal investigator or his/her designee at each transplant center will contact the candidates and enroll them onto the study. The study coordinator at each center will provide the patient with information about the purpose of the study and obtain consent. The PIs of the study will provide a template of the consent form to each center that can be customized according to their local requirements and submit it for review by the local Internal Review Board (IRB). Each center must provide evidence of IRB approval.

Confidentiality: Confidentiality will be maintained by individual names being masked and assigned a patient identifier code. The code relaying the patient's identity with the ID code will be kept separately at the center. The ID code will be transmitted to the center that keeps all the clinical data (separate from the center that keeps the biological data).

Participation of women, children, minorities and other populations: Women, children and ethnic minorities will be included in this study.

Accrual will be monitored within each center with the expectation that the enrolled patient population is representative of the transplanted patient population at each center. Representation will be examined by comparing gender, race, ethnicity and age distributions. Accrual of minority patients will be expected to be in proportion to the number of minorities patients transplanted at each center.

11. APPENDIX C: STATISTICS

Sample Size and Power Calculation. Three clinical endpoints are chosen as the primary hypotheses: D180 Post Therapy non-relapse mortality, D28 post-therapy non-response, and GVHD grade 1-4 onset. Seven biomarkers will be tested at either onset of GVHD or at day 14 post-HCT (median 14 days prior GVHD) in predicting these clinical endpoints. Therefore, the overall type-I error is justified by a fact of 7*3*2 = 42, and the per comparison type I error is controlled at 0.05/42 = 0.0012. The effect size is pre-specified by the expected sensitivity and specificity of a biomarker, which ranges from 0.60 to 0.70. The following table present the power of our study (N = 350) for three clinical endpoints. It shows that we shall have more than 91% power to test our hypotheses. Given the fact that our preliminary data show that one biomarker has a 85% sensitivity and specificity, our proposed sample size will have sufficient power to test our hypothesis.

Response Type and Rate	Sensitivity and Specificity		
	0.60	0.65	0.70
D180 Post Therapy non-relapse mortality (0.26)	0.91	>0.99	>0.99
D28 post-therapy non-response (0.41)	0.96	>0.99	>0.99
GVHD grade 1-4 onset (0.50)	0.98	>0.99	>0.99

Our 'pre-specified' expected sensitivity and specificity are based on our previous work (taking the median as cutoff) (see Table below, Vander Lugt et al. NEJM, 2013)

Sonsitivity and	l snacificity of	ST2 concentrations at	D14 to predict	six-month n	ost-HCT NRM
Sensitivity and	i specificity of	SIZ CONCENTRATIONS at	D 14 to predict	six-monui p	

0.1.1	Sensitivity	Specificity
Cutoff	(95% CI)	(95% CI)
75 th percentile	54% (50-59%)	83% (77-89%)
Median	75% (71-79%)	56% (48-64%)
25 th percentile	92% (89-94%)	29% (22-36%)

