2.3. Accrual objective and period

- Accrual objective: Sample size 430
- Accrual period: The estimated accrual period is 24 months

2.4. Study duration: Patients will be followed for 12 months following initiation of GVHD therapy or 12 months post-HCT for non-GVHD patients.

- This study will not require any extra clinic visits beyond those required for routine clinical patient care.
- For subjects who consent to the future unspecified use of their biospecimens for research purposes, clinical data collected at any time post-transplant as part of routine clinical care may also be accessed.

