Progression is defined as deterioration in at least one organ without any improvement in others.

No response (NR) is defined as absence of any improvement or progression as defined. Patients receiving secondary therapy (including need to re-escalate steroid dose to \geq 2.5 mg/kg/day of prednisone or equivalent 2 mg/kg/day of methylprednisolone will be classified as non-responders.

Proportion of complete response (CR), Partial response (PR), mixed response (MR), progression, and no response (NR) at day 28 post-therapy (among surviving patients). Scoring of CR, PR, MR, progression, and NR are in comparison to the patient's acute GVHD status on day 0 of systemic therapy for GVHD.

Incidence of additional systemic GVHD therapy given at day 28, and day 56 posttherapy (including for GVHD flare).

Flares are defined as any progression of acute GVHD after an initial response (e.g. earlier CR or PR) that requires re-escalation of steroids or initiation of additional systemic therapy for GVHD.

Steroid dose at day 28 and day 56 post-GVHD therapy

Dose of methylprednisolone will be converted to prednisone by multiplying the methylprednisolone dose by 1.25. Prednisone dose for each patient will be converted to mg/kg. The cumulative prednisone dose for each patient at day 28 will be calculated by adding the doses (end of each week's dose) for each of the four weeks of treatment, divided by the number of days of survival during this interval. The prednisone dose for each patient at day 28 and day 56 will be recorded.

Chronic GVHD is defined per the BMT CTN manual of procedures chapter 2. Symptoms of chronic GVHD if present will be reported using the GVHD symptom record. The incidence of chronic GVHD at 6 and 12 months will be computed.

Non-relapse mortality (NRM) at day 180 post-therapy for GVHD patients and NRM at day 180 post-HCT for patients without GVHD will be computed. The events for NRM are death due to any cause other than relapse of underlying malignancy.

Overall survival, GVHD-free survival at day 180 and 360 post-therapy for GVHD patients and at day 180 and 360 post-HCT for patients without GVHD will be computed.

Relapse at day 360 post-HCT will be computed.

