Official Title: Bridging Pediatric and Adult Biomarkers in Graft-Versus-Host Disease

NCT number: NCT02194439

Document date: 01Feb2020

Study population

The study accrued 415 HCT recipients between 2013 and 2018; 170 children ≤10 years and 245 subjects >10 years, including both children and adults. All subjects were followed for at least 1 year. This study registered at clinicaltrial.gov under NCT02194439 was approved by the respective Institutional Review Boards at six adult and pediatric centers: Children's National Medical Center, Texas Children's Hospital, Fred Hutchinson Cancer Research Center, Boston Children's/Dana Farber Cancer Institute, Johns Hopkins, and Indiana University. Adult patients were solely from two centers. Informed consent was btained from all patients or their legal guardians.

Samples preparation and ELISA

All plasma samples were prospectively collected and stored per institutional guidelines. Frozen samples were shipped to the [name] Laboratory at Indiana University for analysis. ST2, IL6, REG3α, and TNFR1 were measured pre-HCT (day -7) and on days +7, +14, +21 post-HCT as previously examined in the aGVHD setting. All of these biomarkers were measured using sequential enzyme-linked immunosorbent assay (ELISA), as previously reported.

Statistical analysis

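### The power figures at sensitivity = specificity 0.60 do not follow from the stated alpha of 0.0012 and N = 350, and the same 350 is applied to two endpoints that arise only after GVHD therapy

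*Protocol*

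**What the plan says.** Protocol Appendix C, under Sample Size and Power Calculation, counts seven markers, three endpoints and two time points, so that "the per comparison type I error is controlled at 0.05/42 = 0.0012". It then gives one sample size for everything: "The following table present the power of our study (N = 350) for three clinical endpoints". The effect is a sensitivity and specificity between 0.60 and 0.70. The event rates in the table are 0.26 for day-180 post-therapy NRM, 0.41 for day-28 non-response, and, for the third endpoint, "GVHD grade 1-4 onset (0.50)". In the 0.60 column the printed power is 0.91 / 0.96 / 0.98; all other cells read >0.99. The conclusion drawn is "It shows that we shall have more than 91% power to test our hypotheses".

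Protocol section 3.3 sets the populations. For NRM: "Non-relapse mortality (NRM) at day 180 post-therapy for GVHD patients and NRM at day 180 post-HCT for patients without GVHD will be computed". Day-28 response is scored against the patient's "acute GVHD status on day 0 of systemic therapy for GVHD". Section 2.3 has "Accrual objective: Sample size 430", and eligibility (section 2.2) covers allogeneic recipients whether or not they develop GVHD. The SAP reports that "The study accrued 415 HCT recipients between 2013 and 2018" and contains no power calculation.

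**The concern.** There are two separate problems.

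First, a power of 0.91 for a difference of 0.60 against 0.40 in the proportion marker-high, with 91 events among 350, is about what an unadjusted alpha of 0.05 would give. It looks too high for an alpha 42 times smaller.

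Second, 350 cannot be both the whole transplanted cohort, half of whom get GVHD, and the number evaluable for outcomes counted from the start of GVHD therapy.

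The power statement is taken from the 0.60 column, the low end of the plan's own effect range. A reader who relies on it would treat a null result for a modest marker as near-conclusive when it is not, most of all for the two post-therapy endpoints.

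**Working it through.** **Inputs (Appendix C).** Alpha 0.05/42 = 0.00119; N = 350; event rates 0.26, 0.41, 0.50; sensitivity = specificity = 0.60. Order throughout: NRM / day-28 non-response / GVHD onset. The test is not stated, so two models were used.

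**Model A, dichotomised marker.** Compare the proportion marker-high in patients with the event (0.60) and without it (0.40). With n1 = N × rate and n2 = N − n1:

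power = Φ[(0.20 − z × SE0) / SE1], where SE0 uses the pooled proportion, SE1 the separate proportions, and z = 3.241 (two-sided).

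For NRM, n1 = 91 and n2 = 259:
- pooled proportion = (91 × 0.60 + 259 × 0.40)/350 = 0.452
- SE0 = √(0.452 × 0.548 × (1/91 + 1/259)) = 0.06065
- SE1 = √(0.24 × (1/91 + 1/259)) = 0.05970
- power = Φ[(0.20 − 0.1966)/0.0597] = Φ(0.057) = 0.523

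The unpooled version uses SE1 in both places.

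**Model B, continuous marker (more favourable).** Two normal distributions with equal SD and the cutoff midway between them, so d = 2 × 0.2533 = 0.507. For NRM the noncentrality is 0.507 × √(91 × 259/350) = 4.16 against a critical t of 3.27, giving power 0.812.

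**Attempt to reproduce the printed row (0.60 column, N = 350, alpha 0.05/42):**

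| Test | NRM | Day-28 non-response | GVHD onset |
|---|---|---|---|
| Printed | 0.91 | 0.96 | 0.98 |
| A, pooled, two-sided | 0.523 | 0.674 | 0.695 |
| A, unpooled, two-sided | 0.543 | 0.697 | 0.718 |
| A, unpooled, one-sided | 0.622 | 0.764 | 0.783 |
| Rank test, simulated, two-sided | 0.779 | 0.892 | 0.916 |
| B, t-test, two-sided | 0.812 | 0.917 | 0.928 |
| B, t-test, one-sided | 0.863 | 0.944 | 0.953 |

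Continuity-corrected, arcsine, log odds ratio and exact chi-square versions of Model A do no better than its unpooled version.

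**What comes close.** Two changes of input land within about 2 points of the printed row:
- two-sided alpha 0.05, N = 350, Model A pooled: 0.913 / 0.961 / 0.966
- alpha 0.05/42, N = 430, Model B: 0.910 / 0.971 / 0.976

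Each contradicts a figure stated in Appendix C. The documents do not show which, if either, was used.

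**Total N needed for the printed 0.60 cells at alpha 0.05/42 (two-sided).** Model A: 655–670 / 619–635 / 673–690. Model B: 431 / 407 / 443.

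**Other columns at N = 350.** At 0.65, Model A pooled gives 0.964 / 0.992 / 0.994 and Model B is above 0.99 throughout, so only the NRM cell under Model A misses. At 0.70 every cell exceeds 0.99.

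**Evaluable patients for the post-therapy endpoints.** The documents give no expected number treated. Assume it equals the table's own GVHD rate times N, with every such patient treated and sampled: 350 × 0.50 = 175, or 430 × 0.50 = 215. Fewer would lower power further. Two-sided, alpha 0.05/42 (ranges under A are pooled to unpooled):

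| Treated | Sens = spec | NRM, A | NRM, B | Non-response, A | Non-response, B |
|---|---|---|---|---|---|
| 175 | 0.60 | 0.18–0.19 | 0.37 | 0.26–0.28 | 0.50 |
| 215 | 0.60 | 0.25–0.27 | 0.49 | 0.36–0.38 | 0.64 |
| 175 | 0.65 | 0.61–0.66 | 0.88 | 0.76–0.80 | 0.96 |
| 215 | 0.65 | 0.75–0.79 | 0.95 | 0.87–0.90 | 0.99 |
| 175 | 0.70 | 0.94–0.97 | >0.99 | 0.98–0.99 | >0.99 |

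For the printed >0.99 at 0.65, even Model B needs at least 277 treated patients for NRM (277/350 = 79%) and 222 for non-response (222/350 = 63%), against a tabulated GVHD rate of 50%.

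**The case against.** - **The size of the gap depends on a test the plan does not name.** This is correct. Under the one-sided continuous test the shortfall is 2 to 5 points; under the two-sided dichotomised test it is 26 to 39. Appendix C describes its expected values as based on a median cutoff, which favours the dichotomised reading, but it does not settle the matter. What stands under every version tried is that the printed row is not reached.
- **Stronger markers remain well powered.** Also correct at N = 350. The 0.70 column holds, 0.65 is at least 0.96 everywhere, and the plan's own median-cutoff values (sensitivity 0.75, specificity 0.56) give about 0.98 or more under Model A. Appendix C also cites a marker with 85% sensitivity and specificity. But the plan chose 0.60 as the bottom of its range and took its power statement from that column.
- **The treated number is assumed.** True: 175 and 215 are illustrations. Section 3.3 also words the NRM population as GVHD patients rather than treated patients, although the endpoint's post-therapy label and the day-28 definition point to treated patients. The firm point is that no evaluable N is given and that 350 cannot serve all three rows.
- **The SAP does not list either post-therapy endpoint.** It plans landmark analyses of NRM and acute GVHD from markers at day −7 to day +21. That lowers the practical weight, because it plans no result for those endpoints to be read against Appendix C. It does not correct the protocol's figures.

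**Conclusion.** The concern holds on both counts. The 0.60 row of the power table does not follow from alpha 0.05/42 and N = 350 under any test tried: the NRM cell is 0.52 to 0.86 against a printed 0.91, non-response 0.67 to 0.94 against 0.96, and GVHD onset 0.70 to 0.95 against 0.98. That range runs from the pooled two-sided dichotomised test to the one-sided continuous one. Whether the alpha or the N is mislabelled cannot be told from the documents.

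Independently of this, the denominator is wrong for two of the three primary endpoints. How far power falls depends on the number treated. At half the cohort it reaches 0.18–0.64 in the 0.60 column and also pulls the 0.65 column below its printed values. The figures assume equal sensitivity and specificity, the table's event rates, and, for Model B, normal marker distributions with equal spread. The matter should be fixed, but it concerns the stated justification; the SAP reports accrual as complete, so the design itself cannot change.

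**What to change.** In Appendix C:

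1. Name the test and its sidedness.
2. Give the expected evaluable N for each endpoint: treated GVHD patients for the two post-therapy endpoints, all patients for GVHD onset.
3. Say whether the basis is 350 or the accrual target of 430, and how one leads to the other.
4. Recompute the table at alpha 0.05/42 with those inputs.
5. Replace the single power statement with the recomputed figures, each tied to its endpoint and effect size.

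The cost is a recalculation and a rewritten paragraph, with no extra patients or samples. The only drawback is a less favourable stated power.

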We first performed an IPAS comparing pooled plasma taken at D16 ± 5 post-therapy from 10 responders (R) and 10 non-responders (NR). Ten candidate biomarkers with an NR/R ratio of > 1.5 in the IPAS were measurable by ELISA. We therefore measured concentrations in the 20 individual plasma aliquots. Five were significantly increased in NR vs. R, with an area under the receiver operator characteristic curve of ≥ 0.85 (ST2, IL1sRII, MIF, LYVE, and Lipocalin). These were then measured at therapy initiation (D0), with 6 previously validated diagnostic biomarkers of GVHD (IL2R α , TNFR1, HGF, IL8, Elafin, a skin-specific marker, and Reg3 α , a gut-specific marker) in plasma samples from a validation set of 381 patients with acute GVHD grade 1-4 at onset and treated with systemic steroids at the University of Michigan from 2000 to 2011. Preliminary analyses (not shown) determined that D0 measurements predicted D28 non-response and D180 OS. HLA match (match vs. mismatched; Odds Ratio (OR) 1.5, p = 0.07), conditioning intensity (full vs. reduced; OR 1.7, p = 0.04), and GVHD onset grade (grade

3-4 vs. grade 1-2; OR 2.2, p = 0.001) predicted day 28 non-response in univariate analysis, while age at transplant (\geq 55 years vs. < 55 years), donor (unrelated vs. related), and stem cell source (peripheral blood vs. bone marrow/cord) did not. After adjustment for the 3 clinical characteristics which predicted D28 response, multivariate analysis of the 11 protein concentrations showed that 3 predicted D28 response (ST2, p

= 0.001; IL1sRII, p = 0.07; and IL8, p = 0.03) and 7 predicted post-therapy D180 OS (ST2, p = 0.003; IL1sRII, p = 0.07; IL8, p = 0.05; Elafin, p = 0.06; MIF, p = 0.04; TNFR, p = 0.03; and Reg3 α , p = 0.002 in gut-GVHD subset). Using logistic regression, we examined the ability of both the 7 biomarkers and ST2 alone to predict for D28 non- response, as ST2 was the most significant marker in all previous analyses. ST2 is the IL33 receptor, a member of the IL1/ToII-like receptor superfamily, which promotes a Th2-type immune response in

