diseases such as arthritis and asthma ²⁹. A high biomarker value was defined as a plasma concentration greater than 50% above the median value of the responders' group. A high panel was defined as having at least 5 of 7 high biomarkers. Patients with high ST2 levels were 2.6 times more likely not to respond to therapy independent of the aforementioned significant clinical 0.001) while characteristics (p < patients with a high panel were only 1.9 times more likely not to

respond (p = 0.004). Thus, only ST2 measurement was used for further analyses. Because ST2 concentrations correlated with response, we hypothesized that ST2 would predict D180 non-relapse

mortality (NRM), independent of GVHD onset grade, the strongest clinical predictor of NRM (20% for GVHD grade 1-2 vs. 50% for GVHD grade 3-4, Hazard ratio (HR) 3.0, p

< 0.001). NRM cumulative incidence curves and HR for the 4 risk categories of low ST2 / grade 1-2, low ST2 / grade 3-4, high ST2 / grade 1-2, and high ST2 / grade 3-4 are shown in Figure 4. Interestingly, patients presenting with high clinical grade and low ST2 had a good prognosis, suggesting that ST2 provides important prognostic information at initiation of therapy above the clinical grade.

In conclusion, soluble ST2, the form measured by ELISA, is a decoy receptor that drives the Th2 phenotype toward Th1, a mechanism by which it may act in the pathophysiology of resistant GVHD. ST2 concentrations obtained at initiation of GVHD therapy significantly enhance the accuracy of outcome prediction independent of GVHD grade. Measurement of ST2 may allow for early identification of patients at risk for subsequent non-response and mortality, and may provide a promising target for novel therapeutic interventions.

These six diagnostic biomarkers interleukin-2-receptor-alpha, tumor-necrosis-factorreceptor-1, interleukin-8, hepatocyte growth factor, elafin, regenerating islet-derived 3alpha, and suppression of tumorigenicity 2 (ST2) have not been validated blindly in samples from different institutions. We therefore hypothesized that this seven GVHD biomarker panel, measured during the transplant course, would help diagnose GVHD from other post-HCT complications, discriminate between therapy-responsive and unresponsive patients and predict survival in samples prospectively obtained on a multicenter trial.

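### Appendix C calls the sample size sufficient on an unsourced 85%/85% marker, while its power table does not hold at the stated alpha; the ST2 table's interval denominators also appear swapped

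*Protocol*

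**What the plan says.** The sample size text in Protocol Appendix C sets three primary endpoints and divides alpha over 42 comparisons, so that "the per comparison type I error is controlled at 0.05/42 = 0.0012". Whether the test is one- or two-sided is not stated. The effect size is the "expected sensitivity and specificity of a biomarker, which ranges from 0.60 to 0.70". Power is tabulated under the sentence "The following table present the power of our study (N = 350) for three clinical endpoints", whereas section 2.3 gives "Accrual objective: Sample size 430". At sensitivity = specificity = 0.60 the printed power is 0.91 for D180 NRM (rate 0.26), 0.96 for D28 non-response (rate 0.41) and 0.98 for GVHD onset (rate 0.50). From this the text claims power above 91%.

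It then adds "Given the fact that our preliminary data show that one biomarker has a 85% sensitivity and specificity" and concludes that the sample size is enough. A second table, said to be the basis of the planned effect size, gives ST2 at day 14 against six-month post-HCT NRM:

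| Cut-off | Sensitivity (95% CI) | Specificity (95% CI) |
|---|---|---|
| 75th percentile | 54% (50-59) | 83% (77-89) |
| Median | 75% (71-79) | 56% (48-64) |
| 25th percentile | 92% (89-94) | 29% (22-36) |

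The only other 0.85 is in section 1.3, where five candidate proteins separated 10 non-responders from 10 responders "with an area under the receiver operator characteristic curve of ≥ 0.85". Those samples were taken around day 16 after therapy began.

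**The concern.** A reader is told that the sample size is adequate because of a marker far stronger than the planning range. That marker is not identified, and the figures that are shown are much weaker. If the power table stood by itself, the sentence would be surplus. It matters because the 0.60 column does not follow from the alpha that the same paragraph sets, so at the low end of the planned range the 85% claim is the only remaining support for sufficiency.

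The ST2 table is offered as the empirical basis for planning. Its sensitivity intervals are tighter than its specificity intervals, which would be odd for an endpoint that occurs in a minority of patients. If the denominators were exchanged, sensitivity is shown as more precise than it is.

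**Working it through.** **1. The power table.** Inputs, all from Appendix C: N = 350; alpha = 0.05/42 = 0.00119; sensitivity = specificity = 0.60; event rates r = 0.26, 0.41, 0.50. Assumed test: the share with a high marker among patients with the event (p1 = 0.60) against those without (p2 = 1 − 0.60 = 0.40), with n1 = 350r and n2 = 350(1 − r).

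- Pooled share: pbar = (n1·p1 + n2·p2)/350
- s0 = sqrt[pbar(1 − pbar)(1/n1 + 1/n2)]
- s1 = sqrt[p1(1 − p1)/n1 + p2(1 − p2)/n2]
- Power = Φ[(p1 − p2 − z·s0)/s1]

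For r = 0.26: n1 = 91, n2 = 259, pbar = 0.452, s0 = 0.0606, s1 = 0.0597.

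- Two-sided 0.05 (z = 1.960): (0.20 − 0.1189)/0.0597 = 1.359, power 0.913. This reproduces the printed 0.91.
- Two-sided 0.05/42 (z = 3.241): (0.20 − 0.1966)/0.0597 = 0.057, power 0.523.

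| Rate | Printed | Two-sided 0.05 | Two-sided 0.05/42 | One-sided 0.05/42 |
|---|---|---|---|---|
| 0.26 | 0.91 | 0.913 | 0.523 | 0.604 |
| 0.41 | 0.96 | 0.961 | 0.674 | 0.745 |
| 0.50 | 0.98 | 0.966 | 0.695 | 0.764 |

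Unpooled variance, arcsine, continuity-corrected and Fisher versions at two-sided 0.05/42 give 0.47-0.54, 0.63-0.70 and 0.65-0.72. With N = 430 the pooled version gives 0.66, 0.81 and 0.82. At 0.65/0.65 and N = 350 the results are 0.964, 0.992 and 0.994, so the first of these cells is also overprinted as above 0.99. At 0.70 power is essentially 1 throughout.

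**2. The 85% figure against what is shown.** Youden's index (sensitivity + specificity − 1) is 0.70 for 85/85. For the three ST2 rows it is 0.37, 0.31 and 0.21. An AUC is not a sensitivity/specificity pair: under a binormal model, 0.85 corresponds to about 77/77, and 85/85 needs about 0.93. At a median cut with 26% events, specificity cannot exceed 0.50/0.74 = 0.676 even if sensitivity is 1, so 85/85 is out of reach for NRM at that cut. At a 50% event rate it is arithmetically possible, since 0.5 × 0.85 + 0.5 × 0.15 = 0.50.

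**3. Power at the ST2 median-cut values.** Putting p1 = 0.75 and p2 = 1 − 0.56 = 0.44 in the same formula at two-sided 0.05/42 and N = 350 gives 0.980, 0.997 and 0.998. D180 post-therapy NRM and D28 response exist only in treated GVHD patients. The documents do not give that number. Assuming the 50% onset rate, and that all of these patients are treated, it is 0.50 × 350 = 175 to 0.50 × 430 = 215. NRM power is then about 0.66 to 0.80.

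**4. The ST2 intervals.** If the intervals are binomial, n = p(1 − p)(1.96/half-width)².

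- Sensitivity, median cut: 0.75 × 0.25 × (1.96/0.04)² = 450. The 75th and 25th percentile rows give 471 and 452.
- Specificity, median cut: 0.56 × 0.44 × (1.96/0.08)² = 148. The other rows give 151 and 161.

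Taken literally, about 450/(450 + 150) = 75% had six-month NRM. The cut-offs are percentiles, though, so the share above each is fixed. Solving sensitivity·q + (1 − specificity)(1 − q) = share above the cut for the event share q:

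- 75th percentile: (0.25 − 0.17)/(0.54 − 0.17) = 0.216
- Median: (0.50 − 0.44)/(0.75 − 0.44) = 0.194
- 25th percentile: (0.75 − 0.71)/(0.92 − 0.71) = 0.190

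Rounding of the inputs widens this only to 0.17-0.23. At 75% events, 45%, 67% and 87% would lie above the cuts. At 25% events the shares are 26%, 52% and 76%, close to the nominal 25%, 50% and 75%.

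With the denominators exchanged, the median-cut Wald intervals are:

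| Events / non-events | Sensitivity | Specificity |
|---|---|---|
| 150 / 450 | 68-82% | 51-61% |
| 120 / 480 | 67-83% | 52-60% |
| As printed | 71-79% | 48-64% |

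**The case against.** The power claim is made first from the 0.60-0.70 table, which does not use 85%, and the effect size is said to rest on the ST2 table. At the ST2 median-cut values, with all 350 evaluable, power at 0.05/42 is at least 0.98. The case for sufficiency could therefore be made without the 85% sentence. That stands, but it is not the argument the appendix prints, and it depends on 350 evaluable patients for endpoints defined only after GVHD therapy.

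A reader might infer that the protocol's own figures contradict the 85% claim. They do not go that far. The marker, endpoint, time and cut-off are unnamed, the ST2 table covers one marker, one day and one endpoint, and several figures, including the ROC curves in section 1.3, are absent from the text reviewed. The claim is unsupported and out of line with what is shown, and no more than that.

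A reader might also set the odds ratio implied by 85/85, (0.85/0.15)² = 32, against the validation results in section 1.3, where ST2 gave 2.6 and "patients with a high panel were only 1.9 times more likely not to" respond. From the latter one could derive an effect of 0.58, below the planning range. This is not a like-for-like comparison. Those results are adjusted for clinical factors and use a different cut-off, and one ratio fixes a sensitivity/specificity pair only if the two are assumed equal. The 1.9 also belongs to a five-of-seven panel that was not carried forward in that work, while Appendix C powers individual markers.

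On the intervals, the table is attributed to a publication, and the documents give no counts or interval method. The inference needs binomial intervals and percentiles of the same cohort. It is strong because all three rows agree, but it remains to be checked against the source.

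**Conclusion.** The point holds in three parts of unequal weight.

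- The 85%/85% statement has no support in the readable documents and should not carry the sample size conclusion.
- The 0.60 column does not follow from the stated alpha. Power is about 0.52, 0.67 and 0.70 (two-sided 0.05/42, N = 350, two-proportion comparison), not 0.91, 0.96 and 0.98. The printed values match an unadjusted two-sided 0.05 to within 1.4 percentage points. Choosing a one-sided test or another standard test does not close the gap.
- The ST2 interval denominators appear to be swapped, given the two assumptions above. Correcting them would widen the sensitivity intervals and narrow the specificity intervals.

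It would be wrong to conclude that the interval error weakens the power calculation, because no power figure uses those intervals and the point estimates are unchanged. Nor does any of this show the study to be underpowered at every plausible effect: from 0.65 upwards, with all 350 evaluable, power at 0.05/42 is at least 0.96.

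**What to change.** Delete the 85% sentence, or replace it with the ST2 median-cut figures (75%/56%) and the power they give at 0.05/42: 0.98, 0.997 and 0.998 if all 350 are evaluable. State beside it the number expected to be evaluable for the endpoints confined to treated GVHD patients, with the lower power that follows (about 0.66-0.80 for NRM under the assumed 175-215). Restate the whole power table at 0.05/42, and name the test and its sidedness.

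Check the six ST2 intervals against the source counts and recompute them with patients who had NRM as the sensitivity denominator and patients who did not as the specificity denominator.

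The cost is one sentence, one recalculated power table and six intervals, and no new data are needed. The 0.60 column will look clearly less favourable. The SAP reports that accrual is complete at 415, so the change affects how the planned power is described and how null results are read, not enrolment.
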